7.2 EFFORTS TO MINIMIZE BIAS

Randomization tables will be generated by the study Biostatistician and uploaded into the study REDCap database by the UNC Research Coordinator prior to launching data collection. Participants are randomized (1:1) to receive either the RISE Guide (experimental) condition or Breathe2Relax (control) condition after completing their 1-week survey. The list of assignments will be stored securely in REDCap.

Participants will *not* be masked to their study conditions, as branding is visible in both RISE Guide and Breathe2Relax. Moreover, the UNC Research Coordinator will not be masked to condition, as they will be responsible for tracking RISE Guide progress and managing participant payments. The Principal Investigator, Biostatistician, Site Principal Investigators, Site Research Associates, and anyone involved in data analysis will remain masked to condition until data analysis is complete; masking will be maintained through reduced data viewing privileges in REDCap.

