6.1.3 EMERGENCY DEPARTMENT (ED) VISIT

Providers will page the site research associate (RA), who will approach potentially eligible patients and describe the study. Alternatively, the providing Sexual Assault Nurse Examiner may be the site research associate. Interested and eligible participants will provide written informed consent and complete the assessments described below. Assault characteristics and past and prescribed medications will be abstracted from the medical record. EMAs will begin the day after the ED visit.

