6.1.4 STUDY CONFIRMATION

Women who complete their one-week follow-up survey will be randomized and sent a wrist wearable.

The research coordinator will use REDCap, a secure survey platform, to randomize confirmed participants to the active or control condition. EMAs (for all participants), EMIs (for active participants) and RISE Guide (for active participants) will be delivered via Qualtrics, a smartphone-accessible, secure survey website that saves users' progress and automatically sends SMS reminders on a predetermined schedule based on progress. The research coordinator will email the participant instructions for bookmarking her personalized Qualtrics link to her phone, allowing it to appear as an icon (similar to an app) so the participant can click the link and return to it as desired. Qualtrics will automatically send EMAs/EMIs via SMS and provide access and SMS reminders to complete their assigned interventions.

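### The role that randomizes participants also uploads the full allocation list, with no stated barrier to its knowing upcoming assignments, and the list's author is declared masked on the strength of REDCap viewing rights alone

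*Combined protocol and SAP*

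**What the plan says.** Section 7.2 describes how the list is made and loaded: "Randomization tables will be generated by the study Biostatistician and uploaded into the study REDCap database by the UNC Research Coordinator", before data collection is launched. Section 6.1.4 says who assigns: "The research coordinator will use REDCap, a secure survey platform, to randomize confirmed participants to the active or control condition". The trigger is in the same section: "Women who complete their one-week follow-up survey will be randomized and sent a wrist wearable". The schedule in Section 2.6 gives this step a window of days 7 to 21.

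On masking, Section 7.2 states that "the UNC Research Coordinator will not be masked to condition", because that role tracks RISE Guide progress and handles payments. It then says "The Principal Investigator, Biostatistician, Site Principal Investigators, Site Research Associates, and anyone involved in data analysis will remain masked to condition" until the analysis is finished.

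Two safeguards are given, both in Section 7.2: "The list of assignments will be stored securely in REDCap", and "masking will be maintained through reduced data viewing privileges in REDCap".

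Recruitment is done by other people at another time. Section 6.1.3 says "Providers will page the site research associate (RA), who will approach potentially eligible patients and describe the study". Section 9.1 adds that allocation is 1:1, balanced and stratified by site. It gives no block size and no concealment procedure.

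**The concern.** Concealment means that whoever can influence which woman is assigned next does not know what the next assignment is. Here one role handles the whole list before launch and later makes the assignments. That role is openly unmasked, and the text does not say that it is prevented from reading ahead. Secure storage protects the list from outsiders. It says nothing about the person who loaded it.

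The second difficulty is internal to Section 7.2. The role that writes the list is declared masked, and the only mechanism offered is a limit on what can be viewed in REDCap. The biostatistician's knowledge of the sequence would come from generating it, not from viewing it in REDCap.

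Participants are unmasked too, so concealment at assignment carries more of the protection for any comparison between arms. The trial is also a pilot for a larger efficacy trial (Section 6.2), so a loose procedure could be carried forward.

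**Working it through.** The plan states no figure on this point, so there is none to reproduce. The check is mainly of roles, followed by three short calculations to size the exposure.

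**1. Roles side by side**

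| Task | Role | Declared masked? |
|---|---|---|
| Generates the tables (7.2) | Biostatistician | Yes |
| Uploads the tables (7.2) | UNC Research Coordinator | No |
| Randomizes (6.1.4) | Research coordinator | No |
| Approaches and consents women (6.1.3) | Site research associate | Yes |

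Rows 2 and 3 name the same role. That it is the same individual is the natural reading, but it is not explicit. Row 1 is where the masking statement conflicts with the task.

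**2. What can still be influenced.** Eligibility and consent are settled at the emergency visit by masked staff. What remains is the 1-week step: how hard a survey is pursued, when a participant is confirmed, and in what order women within a site are randomized. Section 6.8.4 plans early contact and extra effort near the end of a window. Section 4.1.1.1 has a Lead Research Coordinator review self-report data every two weeks. If that is the same role, prognostic information is also to hand.

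**3. Room to reorder.** Inputs: a goal of 2 to 4 recruits per month (Sections 2.1 and 9.1.2), two sites (Section 2.1), and a window of 21 − 7 = 14 days (Section 2.6). Assuming an equal split, each site stratum recruits 1 to 2 women per month. With 14/30.4 = 0.46 of a month, 0.46 × 1 = 0.46 to 0.46 × 2 = 0.92 women per stratum are in the window on average. Reordering usually needs two women waiting in one stratum, so the opportunity is limited.

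**4. What reading the list would add.** Block sizes are assumed here, because the plan gives none. Someone who sees only past assignments in a stratum, and guesses the arm with more slots left in the block, is right 75.0% of the time for blocks of 2, 70.8% for 4, 68.3% for 6 and 66.6% for 8. Someone who can read the list and knows the order is right 100% of the time.

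**5. A ceiling on the bias.** Suppose a fraction f of women is steered, with those in the upper half of a normal outcome sent to one arm and those in the lower half to the other.

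- Mean of the upper half of a standard normal: √(2/π) = 0.798. The halves differ by 2 × 0.798 = 1.596 SD.
- Bias = f × 1.596: 0.08 SD at f = 0.05, 0.16 SD at 0.10 and 0.32 SD at 0.20.
- For scale, Section 2.1 expects 150 − 37 = 113 women with complete data, or about 56 per arm. The 95% confidence half-width for a mean difference is 1.96 × √(2/56) = 0.37 SD.

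The fractions have no source in the documents, and the formula supposes perfect sorting on the eventual outcome.

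**6. Which analyses are exposed.** Section 9.1.1 makes the primary Aim 1 hypothesis a test of mean scores against fixed cut-offs (30 for the CEQ, 40 for the TAAS), with the control comparison as an addition. Recruitment and retention in Section 9.1.2 are counts and rates against goals. The results that need comparable arms are the secondary acceptability comparison and the count of adverse events by condition.

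**The case against.** The strongest reply is that REDCap holds the list and executes the assignment, and that nothing in the plan says the coordinator can see what comes next. The file might be coded or locked after upload. Recruiters are masked and act about a week earlier, women complete the triggering survey themselves, and few are waiting at any time. The trial does not test efficacy outcomes (Section 6.2), and its main acceptability question does not rest on the control arm.

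Most of this stands, and it limits the size of the problem. It does not supply the missing barrier. Section 7.2 relies on viewing privileges to mask other roles but states no such limit for the coordinator, and it describes a procedure that passes the complete list through that role's hands.

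Two stronger readings are tempting. A reader might infer that allocation is not concealed and that every assignment is predictable. That would require the list to be readable at the time of assignment, and the documents do not say so. A reader might also infer that the biostatistician's masking is false. Knowing the sequence reveals a woman's arm only if list positions can be linked to participants. Site strata and survey dates make that plausible, but the plan does not say that such a link is available to the biostatistician.

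**Conclusion.** The point holds in a limited form. The plan does not show that the assigning role is kept from knowing upcoming assignments, and the masking claimed for the list's author is unsupported by the only mechanism offered. The exposure lies at the 1-week step and bears on the secondary between-arm acceptability comparison and the adverse event tally by condition.

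Its size cannot be estimated from the documents. The 0.08 SD for each 5% of women steered is a ceiling under perfect sorting, not a prediction, and the low flow of women per site argues for less. The conclusion assumes that the coordinator named in Sections 6.1.4 and 7.2 is one role, and that no unstated coding or lock already closes the gap. This is a cheap improvement, not a threat to the pilot's main conclusions.

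**What to change.** Make three changes to Section 7.2:

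- Have the table loaded, with arms coded A and B, by the biostatistician who generated it or by another existing team member who does not randomize.
- Set and state REDCap rights so that the coordinator can execute one assignment at a time but cannot view the table. This restriction is what conceals the list from the coordinator, who learns what A and B mean from the first assignments. The coding serves the biostatistician's masking.
- Drop the masking claim for the list-generating biostatistician unless the arm code is withheld from that role. Without coding, having that person do the upload would only bring a role declared masked closer to the allocation.

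The study was planned to start in July 2021, so the change may come too late for some participants. For women already randomized, record who had access to the list, and report that with the between-arm results.

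The cost is a permission setting, a few sentences and possibly a slightly weaker masking statement. No extra staff are needed, and sample size does not change.

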7.3 STUDY INTERVENTION COMPLIANCE

The study database will track RISE Guide module progress and EMI/EMA completion in real time. Compliance is encouraged via reminders to engage with the intervention to participants and bonus compensation for timely module completion and significant EMI/EMA completion. Participants in both the experimental and

control conditions will complete the Treatment Acceptability/Adherence Scale (TAAS)¹⁴⁶ during their 1-week and 7-week follow-ups.

8 INTERVENTION DISCONTINUATION AND PARTICIPANT WITHDRAWAL

8.1 PARTICIPANT DISCONTINUATION/WITHDRAWAL FROM THE STUDY

Participants are free to withdraw from participation in the study at any time upon request. The research team will ask participants to share their reason for leaving the study, though withdrawn participants may elect not to share their reason.

An investigator may discontinue or withdraw a participant from the study for the following reasons:

1. Significant study intervention non-compliance
2. If any clinical adverse event (AE) or other medical condition or situation occurs such that continued participation in the study would not be in the best interest of the participant
3. If the participant meets an exclusion criterion (either newly developed or not previously recognized) that precludes further study participation

The reason for participant discontinuation or withdrawal from the study will be recorded in the study database. Subjects who sign the informed consent form and are randomized, receive the study intervention, and subsequently withdraw, or are withdrawn from the study, will not be replaced.

8.2 ADVERSE EVENTS AND SERIOUS ADVERSE EVENTS

8.2.1 DEFINITION OF ADVERSE EVENTS (AE)

Adverse event means any untoward medical occurrence associated with the use of an intervention in humans, whether or not considered intervention-related (21 CFR 312.32 (a)).

8.2.2 DEFINITION OF SERIOUS ADVERSE EVENTS (SAE)

An adverse event (AE) or suspected adverse reaction is considered "serious" if, in the view of the investigator, it results in any of the following outcomes: death, a life-threatening adverse event, inpatient hospitalization or prolongation of existing hospitalization, a persistent or significant incapacity, or substantial disruption of the ability to conduct normal life functions. Important medical events that may not result in death, be life-threatening, or require hospitalization may be considered serious when, based upon appropriate medical judgment, they may jeopardize the participant and may require medical or surgical intervention to prevent one of the outcomes listed in this definition. Examples of such medical events include expression of a suicidal or homicidal plan.

8.2.3 CLASSIFICATION OF AN ADVERSE EVENT

8.2.3.1 SEVERITY OF EVENT

The following guidelines will be used to describe severity of AE:

- **Mild** – Events require minimal or no treatment and do not interfere with the participant's daily activities.

- **Moderate** – Events result in a low level of inconvenience or concern with the therapeutic measures. Moderate events may cause some interference with functioning.
- **Severe** – Events interrupt a participant’s usual daily activity and may require systemic drug therapy or other treatment. Severe events are usually potentially life-threatening or incapacitating. Of note, the term “severe” does not necessarily equate to “serious”.

8.2.3.2 RELATIONSHIP TO STUDY INTERVENTION

All adverse events (AEs) must have their relationship to study intervention assessed by the clinician who examines and evaluates the participant based on temporal relationship and his/her/their clinical judgment. The degree of certainty about causality will be graded using the categories below. In a clinical trial, the study product must always be suspect.

- **Related** – The AE is known to occur with the study intervention, there is a reasonable possibility that the study intervention caused the AE, or there is a temporal relationship between the study intervention and event. Reasonable possibility means that there is evidence to suggest a causal relationship between the study intervention and the AE.
- **Not Related** – There is not a reasonable possibility that the administration of the study intervention caused the event, there is no temporal relationship between the study intervention and event onset, or an alternate etiology has been established.

8.2.3.3 EXPECTEDNESS

Drs. [name] and [name] will be responsible for determining whether an adverse event (AE) is expected or unexpected. An AE will be considered unexpected if the nature, severity, or frequency of the event is not consistent with the risk information previously described for the study intervention.

8.2.4 TIME PERIOD AND FREQUENCY FOR EVENT ASSESSMENT AND FOLLOW-UP

The occurrence of an adverse event (AE) or serious adverse event (SAE) may come to the attention of study personnel during study visits and interviews of a study participant presenting for medical care.

All AEs not meeting the criteria for SAEs will be captured in the study REDCap database. Information to be collected includes event description, time of onset, clinician’s assessment of severity, relationship to RISE Guide (assessed only by [name]), and time of resolution of the event. All AEs occurring while participating in the study must be documented appropriately regardless of relationship. All AEs will be followed to adequate resolution (assurance of immediate safety and provision of referral to care).

Any medical or psychiatric condition that is present at the time that the participant is screened will be considered as baseline and not reported as an AE. However, the study participant’s symptoms will be recorded as an adverse event if their:

- anxiety severity doubles between assessments *and* falls above the cutoff for moderate anxiety (PROMIS Anxiety $\geq 17^{167}$),
- depression severity doubles between assessments *and* falls above the cutoff for moderate depression, (PROMIS Depression $\geq 23^{167,168}$),
- and/or PTS severity doubles between assessments *and* falls above the cutoff for probable PTSD (PCL-5 $\geq 31^{169}$).

Changes in the severity of an AE will be documented to allow an assessment of the duration of the event at each level of severity to be performed. Documentation of onset and duration of each episode will be maintained for AEs characterized as intermittent.

The research coordinator will record all reportable events that they learn of with start dates occurring any time after informed consent is obtained until 7 (for non-serious AEs) or 30 days (for SAEs) after the last day of study participation. Events will be followed for outcome information until resolution or stabilization (assurance of immediate safety and provision of referral to care).

8.2.5 ADVERSE EVENT REPORTING

Adverse events (AEs) will be tracked within the study's REDCap database. Serious adverse events (SAEs) and AEs that are unexpected or possibly related to participation in the research study will be submitted to IRB as New Safety Information (NSI) within 7 calendar days of the event being brought to our attention. The report of AEs or SAEs will include whether they were expected or unexpected, the severity of the event, a brief narrative summary of the event, a determination of whether a causal relationship existed between the study procedures and the event, whether the informed consent or study procedures should be changed as a result of the event, and whether all enrolled participants should be notified of the event.

9 STATISTICAL CONSIDERATIONS

9.1 STATISTICAL HYPOTHESES

- **Hypothesis 1:** Treatment acceptability for RISE Guide is greater than or equal to treatment acceptability for a relaxation control.
- **Hypothesis 2:** A randomized controlled trial to test the RISE Guide intervention will be feasible. Sample Size Rationale

A balanced, site-stratified randomization scheme (1:1) will be used. We ensured adequate power (.80, $\alpha = .05$) to test all hypotheses by ensuring power for the hypothesis in need of the greatest sample size (mediation effects of the intervention on clinical outcomes via changes in AS). Power analyses were conducted and sample sizes were chosen based on power as well as feasibility of this initial pilot study.

Statistical Analyses

9.1.1 AIM 1 (USABILITY, ACCEPTABILITY, AND CREDIBILITY)

To examine usability, credibility, and acceptability of RISE Guide, mean credibility/acceptability scores will be compared to norms to ascertain treatment credibility/acceptability.

Specifically, mean levels of the Credibility/Expectancy Questionnaire (CEQ)¹⁹⁷ to assess credibility and the Treatment Acceptability/Adherence Scale (TAAS)²¹¹ will be examined to assess acceptability and adherence at 1 week will be compared to published CBT interventions, with the hypothesis that CEQ and TAAS total scores will exceed 30 and 40, respectively. Utilization and acceptability will also be examined via response from the 6 week measure designed for the current study (including 6 items on a 5-point Likert scale, such as *How often did you log in? How interested were you?* and 4 open-ended questions; e.g., *What did you like about RISE Guide?*; *What did you not like?*). Descriptive statistics will be analyzed to determine if any specific area needs improvement. Then, open-ended items will be evaluated by reading and noting important and common feedback, focusing on comments related to ease of use, comprehensibility, limitations, and suggestions for improvement. Scores will be compared to the Relaxation Control condition as well, but the primary Hypothesis is that mean scores will exceed the CEQ and TAAS cut-offs provided above.

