2 PROTOCOL SUMMARY

2.1 SYNOPSIS

Title:	Development of a Digital Therapeutic Targeting Anxiety Sensitivity to Reduce PTS-CUD in Women Presenting for Emergency Care after Sexual Assault
Study Description:	The proposed research aims will test the hypotheses that a highly promising digital therapeutic targeting anxiety sensitivity (AS) will be acceptable to women sexual assault survivors, feasible to deliver, and that an RCT testing it will be feasible to recruit and retain participant for. If successful, this intervention (RISE Guide) could be provided at no cost to all women who present to US EDs for emergency care after sexual assault.
Objectives and Associated Outcome Measures:	
Aim 1. Evaluate usability (TUA), acceptability (TAAS), and credibility (CEQ) of both interventions.
 
• Treatment Acceptability/Adherence Scale (TAAS; 1 week) The TAAS is a 10-item measure of treatment acceptability (e.g., I would recommend this treatment to a friend) and adherence (e.g., I would be able to finish [this treatment]) that participants rate on a 7-point Likert scale.• Credibility/Expectancy Questionnaire (CEQ; 1 week) 6-item measure of treatment credibility and expectancy of treatment to improve symptoms. Items are rated on 9-to-11-point Likert scales.• Treatment Utilization and Acceptability (TUA; 7 week) 6 items created for the current study on a 5-point Likert scale, such as How often did you log in? How interested were you? and 4 open-ended questions; e.g., What did you like about RISE Guide?; What did you not like? 
Aim 2. Assess feasibility of conducting a randomized controlled trial to test the RISE Guide intervention.
 
• Recruitment. Final sample size recruited and number of participants recruited per month will be used to evaluate the feasibility of recruiting the target sample (goal recruitment=2-4 participants per month).• Retention. Final proportion of participants who completed all follow-ups (1 week, 7-week, 6 months) will be used to evaluate feasibility of retaining the target sample (goal retention=75% or higher).• Adverse Events. We will examine whether adverse events occur throughout the study.• •

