6.1.2 PROCEDURE OVERVIEW

Women presenting for emergency care within 72 hours of sexual assault will be enrolled. As in [name] recent large-scale observational study (UNC IRB 13-3193), women will be approached during their initial ED visit. In the 7 weeks after assault, women will complete EMAs to assess PTS, cannabis cravings and use, and wear a wrist wearable to assess EDA. Consistent with [name] observational study, women will complete self-report remote follow-up evaluations 1 week, 7 weeks and, 6 months after assault via online surveys (REDCap).¹³⁷

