6.1.5 MECHANISM ASSESSMENTS

EMAs during the first 7 weeks after assault will assess PTS and cannabis cravings/use. EMAs will be distributed to participants via SMS a total of 4 times per day. Participants will be asked to complete ≥ 2 EMAs/day, as we have found providing additional opportunities to complete EMAs increases compliance rates. Three of the four EMAs will be signal contingent (i.e., occurring at random intervals throughout the day). The 4th will be interval contingent, occurring at the end of the day and assessing 1) total cannabis use quantity for that day and 2) whether the participant engaged in any strenuous physical activity, and when the activity occurred (to

exclude these time periods from physiological data analysis). EMAs are delivered weeks 0-7 for the control, and weeks 0-1 for the active condition, who receive EMAs with EMIs weeks 1-7

Figure 3 Empatica E4 wristband

Participants who complete the 1-week survey will be randomized and receive a wrist wearable (**Empatica E4, worn 6 weeks post-assault**; Figure 3) via mail. This wearable continuously assesses physiologic measures (i.e., EDA), and allows users to press a button to mark occurrences. Participants will be asked to mark occurrences when they experience internal or external trauma reminders (e.g., intrusive memories or external cues). Participants will receive a brief introduction to the wrist wearable in the ED and further instructions at 1 week. Consistent with prior research,¹⁴³ data will be analyzed in 40-min blocks (20 min pre- and post-event triggers) and compared to random 40-min blocks in which triggers did not occur.

EDA will be assessed at 4 Hz from 2 wrist wearable sensors. Data (in MicroSiemens) will be analyzed using Ledalab,¹⁴⁴ a validated software package. Processed and cleaned data will be output for every 500 ms in the 40-min block. To quantify anxious reactivity, peak EDA will be identified from these data and subtracted from average EDA in the corresponding “baseline” interval. *Wearable and EMA data will provide a naturalistic assessment of PTS and cannabis cravings/use, and whether the intervention impacts these variables.* The E4 has been rated as acceptable and positive by substance users, from whom EDA data from the E4 has been successfully used to detect stress and cravings in the natural environment.¹⁴³

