6.1.6 SELF-REPORT ASSESSMENTS

Clinical assessments (Table 2) will occur remotely via REDCap, a reliable and valid method of data collection.¹³⁷ Treatment acceptability will be measured at 1 week via the Credibility/Expectance Questionnaire (CEQ),¹⁴⁵ Treatment Acceptability/ Adherence Scale (TAAS),¹⁴⁶ and 7 weeks with a study-specific measure with open-ended questions. PTS, CUD and secondary outcomes will be assessed at 6 months, allowing for temporal mediation tests. Demographic information will be collected on the one-week survey. Current medication use will be collected at one and seven weeks, and six months.

Table 2. Select Measures by Domain and Time Point

Domain	Measure	ED	EMA	1-wk	7-wk	6-mo	12-mo*
Anxiety	Patient-Reported Outcomes Measurement Information System (PROMIS) - Short Form 8a ¹⁴⁷			X	X	X	
Pre-SA Anxiety	Patient-Reported Outcomes Measurement Information System (PROMIS) - Short Form 8a ¹⁴⁷ , Retrospective				X		
Anxiety sensitivity	Anxiety Sensitivity Index-3 (ASI-3) ⁵²	X		X	X	X	
Depression	PROMIS - Short Form 8b ¹⁴⁷			X	X	X	
Pre-SA Depression	PROMIS - Short Form 8b ¹⁴⁷ , Retrospective			X			
Posttraumatic Stress	PTSD Checklist (PCL-5) ¹⁴⁸ , adapted for assault as index trauma and Ecological Momentary Assessment (EMA) when relevant	X	X	X	X	X	
Stress Reactivity	Empatica E4 (6 weeks post-assault), Positive and Negative Affect Schedule (PANAS) ¹³⁸	X	X				
Substance Use	Composite International Diagnostic Interview Screening Scales (CIDI-SC), daily use and quantity ¹⁴⁹	X	X	X	X	X	
Problematic Cannabis & Substance Use	Cannabis : Marijuana Problems Scale (MPS), ¹⁵⁰ Marijuana Motives Measure (MMM), ¹⁵¹ Marijuana Craving Questionnaire (MCQ) ¹³⁹ ; Other : Alcohol Use Disorder Identification Test (AUDIT) ¹⁵² , Drug Abuse Screening Test (DAST), ¹⁵³ Fagerstrom Test for Nicotine Dependence (FTND) ¹⁵⁴			X	X	X	X
Treatment Credibility / Acceptability	Credibility/Expectancy Questionnaire (CEQ), ¹⁴⁵ Treatment Acceptability/Adherence Scale (TAAS), ¹⁴⁶ study specific measure of usability			X	X		

* Self-report assessments and contact information updates are only conducted at the 12-month (365-393 day) timepoint for participants who consented to this study prior to the timepoint's removal in version 2.4 of this protocol.

6.1.7 3.5 MONTH CONTACT UPDATE

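### Aim 1 rests on 1-week CEQ and TAAS scores that women give before they are randomized, so as written they do not rate RISE Guide

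*Combined protocol and SAP*

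**What the plan says.** **When the instruments are given.** Section 9.1.1 states that the TAAS "will be examined to assess acceptability and adherence at 1 week will be compared to published CBT interventions", with totals above 30 (CEQ) and 40 (TAAS) hypothesized. It adds a comparison with the relaxation control, but states that "the primary Hypothesis is that mean scores will exceed the CEQ and TAAS cut-offs provided above". The synopsis (2.1) lists "Treatment Acceptability/Adherence Scale (TAAS; 1 week" and gives the same time for the CEQ. Section 6.1.6 agrees: "Treatment acceptability will be measured at 1 week via the Credibility/Expectance Questionnaire (CEQ", with the TAAS alongside it and only the study-specific measure at 7 weeks.

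**When women are randomized.** Section 6.1.4: "Women who complete their one-week follow-up survey will be randomized and sent a wrist wearable". Section 6.1.5: "Participants who complete the 1-week survey will be randomized and receive a wrist wearable". Section 7.2 also places the 1:1 randomization after the 1-week survey.

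**What 1 week means.** Section 6.1.2: "women will complete self-report remote follow-up evaluations 1 week, 7 weeks and, 6 months after assault". The clock starts at the assault, not at the start of the intervention.

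**What points to a later score.** Section 7.3 has women in both conditions complete the TAAS at 1 and 7 weeks. In Table 2 the credibility and acceptability row is marked at both times, without showing which instrument is given when. Section 9.1.1 uses neither a 7-week TAAS nor a 7-week CEQ.

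**The concern.** The two questionnaires ask about a treatment: whether it is credible, whether the woman would recommend it, whether she could finish it. At the 1-week survey she has no assigned treatment to answer about. Two analyses are affected.

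- The primary test against 30 and 40 could be passed or failed on ratings by women who have not met RISE Guide.
- The comparison with control would use a variable measured before randomization. Randomization makes its expected difference zero, however well or badly RISE Guide is received.

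Hypothesis 1 is one of only two statistical hypotheses in 9.1, and section 5 ties it to the CEQ and TAAS. A pilot that informs a larger trial could therefore report that RISE Guide is acceptable, or not, from data unrelated to it.

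**Working it through.** The plan gives no SD, effect size, margin or power figure for the CEQ or TAAS, so there is no stated number to reproduce. The main check is the order of events.

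**Step 1. Order of events.**

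| Step | Source |
|---|---|
| Enrolment at the emergency visit | 6.1.3 |
| 1-week survey, timed from assault, with CEQ and TAAS | 2.1, 6.1.2, 6.1.6, 9.1.1 |
| Coordinator randomizes women who completed that survey | 6.1.4, 6.1.5, 7.2 |
| Coordinator emails the personalized link; intervention begins | 6.1.4 |
| 7-week survey, with TAAS (7.3) and usability measure | 2.1, 6.1.6, 7.3 |

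No section describes revealing the arm, or showing either intervention, before or during the 1-week survey. Section 6.2, which explains the design of the larger trial, says the intervention starts at 1 week so that initial symptoms can be compared between groups. That treats 1-week values as baseline, though it concerns symptoms rather than acceptability.

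**Step 2. Comparison with control at 1 week.** For a score Y taken before random allocation, E(Y | RISE Guide) − E(Y | control) = 0. A two-sided 5% test therefore rejects with probability 0.05 at any true post-exposure effect d. Two simulations of 20,000 runs each confirm this:

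- 75 per arm (all 150 randomized), SD 1, pre/post correlation 0.5: the test on the pre-allocation score rejected in 4.7% to 5.0% of runs for d from 0 to 0.8.
- 56 per arm: rejection 4.8%, and the RISE Guide mean was at or above the control mean in 50.2% of runs.

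**Step 3. What a woman with no opinion would score.** The synopsis gives 10 TAAS items on a 7-point scale. It gives 6 CEQ items, of which it says "Items are rated on 9-to-11-point Likert scales". It does not give the coding. Marking every midpoint yields:

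- TAAS: 10 × 4 = 40 if coded 1–7; 10 × 3 = 30 if coded 0–6.
- CEQ: 6 × 5 = 30 for any mix of 1–9 and 0–10 items. The extremes are 6 × 4 = 24 (all items 0–8) and 6 × 6 = 36 (all items 1–11).

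Under the 1–7 coding for the TAAS and the 1–9 or 0–10 coding for the CEQ, the neutral totals equal the two cut-offs. If the true pre-exposure means sat there, each sample mean would exceed its cut-off about half the time. Both would do so with probability 1/4 + arcsin(r)/(2π), where r is the correlation between the two sample means:

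- r = 0: 0.25
- r = 0.5: 0.33
- r = 0.9: 0.43

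**Step 4. What a post-exposure score could detect.** This is illustration only, because d and the number responding are assumptions. The 56 per arm is roughly half of 150 − 37 = 113, the number left after the drop-out expected in the synopsis. Two-sample t-test, two-sided 5%:

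| Responders per arm | Power, d = 0.3 | Power, d = 0.5 |
|---|---|---|
| 40 | 0.26 | 0.60 |
| 56 | 0.35 | 0.75 |
| 75 | 0.45 | 0.86 |

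**The case against.** The order of events in 6.1.4, 6.1.5 and 7.2 is hard to dispute. The counter-arguments concern how far the damage extends.

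- **Later data may already exist.** Section 7.3 schedules a 7-week TAAS, and Table 2 may imply a 7-week CEQ. This stands and makes the repair cheaper. It does not remove the problem, because 9.1.1 never uses those scores and 2.1 gives 1 week as the only time for both instruments.
- **Hypothesis 1 has no time point.** Neither its statement in section 5 or 9.1 nor the control-comparison sentence in 9.1.1 gives one, and the wording of 9.1.1 is garbled. This stands in part: the 1-week reading of the control comparison comes from 2.1 and 6.1.6. No section names a later CEQ or TAAS score for that comparison.
- **It may be wording, not conduct.** Section 7.3 speaks of women in both conditions completing the TAAS at 1 week, which read literally implies that allocation has already happened. That contradicts three other sections. If practice differs from them, the protocol needs to say so.
- **Expectancy can be rated before use.** Some items look forward, and consent forms describe the intervention. Such ratings may carry some information about anticipated credibility. Without an assigned arm they cannot be arm-specific.
- **The numbers are hypothetical.** This stands for steps 3 and 4. The item coding is not given, and nothing in the documents places pre-exposure means at the cut-offs.
- **The origin of 30 and 40 cannot be checked.** Section 9.1.1 cites references 197 and 211, while the list ends at 194. Whether those norms were collected before or after treatment is unknown from the documents.

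**Conclusion.** The concern holds. A stated rule, followed as written, produces the wrong quantity; this is more than missing detail. The conclusion on timing needs no numerical assumption. The 1-week CEQ and TAAS precede allocation, so they cannot support the primary Aim 1 hypothesis as a statement about RISE Guide. Used for the control comparison, they have an expected difference of zero and a rejection rate equal to alpha, about 5%. The 50% and 25% to 43% chances of clearing the cut-offs are conditional on pre-exposure means sitting at 30 and 40, and the match with neutral totals depends on item coding. The usability part of Aim 1 (dated 7 weeks in 2.1 and 6 weeks in 9.1.1) is collected after the intervention begins and can still be answered. This must be fixed, because no analysis can turn pre-allocation ratings into ratings of RISE Guide.

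**What to change.** 1. Reconcile 2.1, 6.1.6, Table 2, 7.2, 7.3 and 9.1.1 on when each instrument is given relative to allocation. If the CEQ and TAAS are in practice given after allocation, state that in 6.1.6 and 7.2.
2. Otherwise, name the 7-week TAAS as the Aim 1 acceptability endpoint, by randomized arm, for both the cut-off of 40 and the control comparison.
3. Give the CEQ soon after allocation and presentation of the assigned intervention, so that it still measures expectancy. A repeat at 7 weeks is optional; check first whether Table 2 already plans it.
4. Use any 1-week CEQ or TAAS scores only as baseline.
5. State the item coding, and confirm that the sources of 30 and 40 used ratings taken at a comparable stage.
6. Report the number randomized beside the number responding, by arm.

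The cost is protocol wording and at most one 6-item questionnaire shortly after allocation, since 7.3 already schedules the 7-week TAAS. If that TAAS is not in fact being collected, the cost is somewhat higher. The drawbacks are a small added burden on participants and some non-response at 7 weeks, whose rate among randomized women the documents do not give.
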